5.12 Visit Specific Procedures

The following sections outline the procedures required at each visit.

5.12.1 Baseline Visit/ Day 1

Prospective subjects will visit the study center and be examined by the study physician. The following procedures will be performed at the baseline visit:

A horizontal bar chart showing the distribution of a variable across 12 categories. The bars are black and of varying lengths, representing the magnitude of the variable for each category. The categories are ordered from highest to lowest value.

5.12.2 Telephone Contact/Week 2/Day 14 (\pm 4 days)

Type of cancer	Percentage
Skin	~35%
Lung	~25%
Breast	~15%
Prostate	~10%
Colon	~8%
Ovarian	~5%
Bladder	~4%
Pancreas	~3%
Stomach	~2%
Esophagus	~1%

5.12.3 Visit 2/Week 4/Day 28 (\pm 4 days)

A horizontal bar chart showing the percentage of patients with a history of stroke or TIA across different age groups. The x-axis represents the percentage from 0% to 100% in 10% increments. The y-axis lists age groups: 18-29, 30-39, 40-49, 50-59, 60-69, 70-79, and 80+ years. The bars are black with white outlines. The percentage increases with age, reaching approximately 75% for the 80+ group.

Age Group	Percentage
18-29	~10%
30-39	~15%
40-49	~20%
50-59	~25%
60-69	~30%
70-79	~45%
80+	~75%

• [REDACTED]

5.12.4 Visit 3/Week 8/Day 56 (\pm 4 days)

5.12.5 Visit 4/Week 12/Day 84 (\pm 4 days) End of Treatment/Early Termination Visit

5.12.6 Unscheduled Visit

An unscheduled visit is allowed at anytime if in the investigator's opinion it is warranted. If the investigator assesses the subject's condition and determines that the subject's condition has worsened to the degree that it is unsafe for the subject to continue in the study, the subject may be discontinued from the study as a treatment failure, and a standard of care treatment may be advised at the investigator's discretion. The following procedures may be performed at the Unscheduled Visit if required.

• [REDACTED]

• [REDACTED]
[REDACTED]
[REDACTED]
[REDACTED]
[REDACTED]

[REDACTED]
[REDACTED]
[REDACTED]

Page 21 of 49

Page 24 of 52

5.13 Summary of Assessments

The schedule of visits and procedures to be conducted at each visit are summarized in the Schedule of Study Procedures.

Protocol No: PRG-NY-15-003

^a Schedule next visit if applicable

^f Study medication to be collected and/ or dispensed, if necessary

5.14 Screen Failures

Screen failures will not be entered in the database and included in any data analyses. A screen failure is a subject who received information about the study, including signing an informed consent, and possibly performing some study related procedures, but was not enrolled, dispensed and applied the investigational product.

5.15 Protocol Deviations/Violations

This study will be conducted as described in this protocol except for an emergency situation in which the protection, safety, and well-being of the subject requires immediate intervention, based on the judgment of the investigator or a responsible, appropriately trained and credentialed professional(s) designated by the investigator. In the event of a significant deviation from the protocol due to an emergency, accident or mistake, the investigator or designee must contact Perrigo / [REDACTED] contacts in Section 15 (Appendix A) at the earliest possible time.

[REDACTED]

[REDACTED]

[REDACTED]

5.16 Subject/Treatment Compliance

Subjects will apply the medication onto six areas of the face (chin, left cheek, right cheek, nose, left forehead and right forehead) at approximately the same time once daily for 12 weeks. On Day 1, subjects will apply their initial dose of study medication [REDACTED]

[REDACTED] On Week 2 Day 14/

(± 4 days), compliance will be assessed via telephone contact. The study coordinator, or designee, will review the Subject Instruction Sheet and Diary with the subject on the phone. The total number of study medication doses applied and/or missed will be determined based upon the first dose applied through and including the last dose applied. The first and last dates of treatment

[REDACTED]

should be recorded on the CRF. The total of applied and missed study medication applications should also be recorded. By definition there are no missed applications before the first date of treatment or after the last date of treatment.

[REDACTED]. All used and unused pump bottles of study medication will be collected by the study site at appropriate visits or early termination.

5.17 Discontinuation/Withdrawal of Study Subjects

Subjects may be removed from the study for any of the following reasons:

- The subject withdraws his or her consent for any reason.
- The subject's condition has worsened to the degree that the investigator feels it is unsafe for the subject to continue in the study.
- The subject's medication code is unblinded.
- Subject did not meet or no longer meets the entry criteria.
- An adverse event including intercurrent illness, occurs for which the subject desires to discontinue treatment or the investigator determines that it is in the subject's best interest to be discontinued.
- The subject is lost to follow-up. The investigator will document efforts to attempt to reach the subject twice by telephone and will send a certified follow-up letter before considering that subject lost to follow-up. All attempts must be thoroughly recorded.
- The subject becomes pregnant during the course of the trial.
- Lack of efficacy (treatment failure) after 4 weeks (30 days) of compliant treatment (investigator removal from study).
- Investigator discretion

After a subject has been discontinued, he/she will not be allowed to re-enroll in the study.

The reasons for a subject being discontinued will be documented in the case report (CRF) form and the enrollment log.

If a subject is discontinued from the study for any reason, the Visit 4 (Day 84)/ End of Study Visit/Early Termination Visit procedures should be completed and any outstanding data and study medication should be collected. Data, in addition to the reason for discontinuation and the date of removal, will be recorded on the Source Document and End of Study Case Report Form.

In the event that a subject discontinues from the study at any time due to an adverse event, the reason for discontinuation, the nature of the event and its clinical course must be fully documented. For such a subject, the investigator must strive to follow the subject until the adverse event has resolved, become clinically insignificant, is stabilized, or the subject is lost to follow-up.

6. MATERIALS AND SUPPLIES

6.1 Study Medication

The study medication supplied by Perrigo will consist of:

Test Product: Clindamycin Phosphate and Benzoyl Peroxide Topical Gel 1.2%/3.75%,

Reference Product: Onexton™ Topical Gel (Clindamycin Phosphate and Benzoyl Peroxide Gel 1.2%/3.75%),

Manufactured by Valeant Pharmaceuticals North America, LLC.

Vehicle: Vehicle of test product

SUPPLIES:

In addition to the study medication, subjects will be given Purpose® gentle cleansing wash to wash their face as instructed and Purpose® dual treatment moisture lotion with SPF 15 to use as instructed.

6.2 Medication Management

6.2.1 Labeling, Packaging and Distribution

The study medication assigned to each subject number will be determined by a computer-generated randomization schedule. Study medication is labeled and packaged, according to the random code, so that neither the subject nor the investigator can identify the treatment.

The tear-off portion of each kit label contains the identity of the medication in the pump bottle. The investigator will not remove the occluding layer of the label unless absolutely necessary to provide medical treatment to a subject in an emergency and preferably with prior authorization from Perrigo or designee, whenever possible. If the occluded portion of the label is removed, each

involved subject(s) will be discontinued from the study and the reason will be noted on the source document and CRFs.

The tear-off portion has an adhesive backing to affix to the study medication dispensing log that will be maintained at the investigator site. The individual boxes are numbered sequentially and should be dispensed in order.

The investigator performing the clinical evaluations will not dispense or collect study medication.

6.2.2 Retention Samples

Each investigational site where study medication is dispensed to at least one subject will be required to randomly select one block of study medication [REDACTED]

[REDACTED] to be maintained as retain samples. The investigator will maintain one randomly selected block of study medication for each shipment of study medication received. As per the Code of Federal Regulations Part 21, Section 320.38(e), "Each reserve sample shall be stored under conditions consistent with product labeling and in an area segregated from the area where testing is conducted and with access limited to authorized personnel (in a refrigerator, 2°C to 8°C (36°F to 46°F) in an upright position) even after the study has concluded. Each reserve sample shall be retained for a period of at least 5 years following the date on which the application or supplemental application is approved, or, if such application or supplemental application is not approved, at least 5 years following the date of completion of the bioavailability study in which the sample from which the reserve sample was obtained was used." The investigator will store the retain sample study medication until such time as notification is received from Perrigo that the samples are no longer required.

6.2.3 Storage and Test Article Accountability

Study medication used to conduct this study will be maintained under adequate security by the investigator or designee. Study medication will be stored in a refrigerator, 2-8°C (36-46°F) in a secured area with limited access. Each investigator site will ensure that the temperature of study medication is monitored and recorded throughout the study. The medication should not be frozen, should be kept in the refrigerator (2-8°C) and kept tightly closed. The investigator will not supply study medication to any person not enrolled in this study, or to any physician or scientist except those named as sub-investigators. Once the pump bottles are dispensed to subjects and exposed to room temperature (RT), they can subsequently be stored at room temperature at or below 25°C (77°F) and the expiration date is 10 weeks only.

Protocol No: PRG-NY-15-003

Each investigator will store at room temperature the Purpose® gentle cleansing wash and Purpose® dual treatment moisture lotion with SPF 15 at the clinic. Upon dispensation the investigator or designee will instruct subjects to store them at home under room temperature.

The clinic personnel will keep a running inventory of study test articles dispensed that will include subject numbers assigned and the date each can of study medication is dispensed, expired and returned. A study medication accountability form will be provided to the investigator to document all medications received, dispensed by and used by each subject. At the conclusion of the study all unused, partially used, and empty containers must be inventoried by the monitor and returned to Perrigo, or designee, for destruction.

6.2.4 Randomization

Randomization will be performed according to a computer generated randomization scheme where the treatment group designation has been assigned to the subject number. The treatment designation will remain blinded until the final database is closed. An independent third party will hold the randomization code throughout the study. The randomization scheme will be a block randomization, with each block of seven subjects assigned to Test: Reference: Vehicle [REDACTED]
[REDACTED]

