5.2 Assignment of Subject Number

As possible an independent third-party dispenser will dispense and assign a subject number to each enrolled subject. The subject number will correspond to a computer-generated randomization schedule assigning the number to one of the three study treatment groups.

Once the subject has consented, met inclusion/ exclusion criteria, they will be assigned a subject number. The subject number will be taken from the study medication kit dispensed to the subject at each site.

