6.2.5 Procedure for Breaking the Blind

The investigator, staff at the study site, study monitors, and data analysis/management personnel are blinded to the subject assignment. In the event of an emergency, the specific subject treatment may be identified by removing the overlay of the blinded label for each subject at each investigator site, which is attached to the study medication log; however, every effort should be made to maintain the blind. **The investigator must not scratch off the occluding layer of the label unless absolutely necessary to provide medical treatment to a subject in an emergency situation only and should seek prior authorization by Perrigo or designee when possible.** The reason for breaking the blind must be clearly documented in the source documentation and CRF and the subject must be discontinued from the study. Perrigo must be notified immediately upon all unblinding situations.

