1 Purpose of Statistical Analysis Plan

The purpose of the statistical analysis plan is to describe in detail all the data, statistical methods, and [summary tables](#) required to implement the statistical analysis of Clinical Study Protocol PRG-NY-15-003 [REDACTED]

2 Study Objectives

To compare the safety and efficacy profiles of Perrigo UK FINCO Clindamycin Phosphate and Benzoyl Peroxide Topical Gel 1.2%/3.75% to Valeant Pharmaceuticals Onexton™ Topical Gel (Clindamycin Phosphate and Benzoyl Peroxide Gel 1.2%/3.75%) and to demonstrate the superior efficacy of the two active formulations over that of the vehicle in the treatment of acne vulgaris.

3 Study Design

For the purpose of exploring the above objectives, the study will be conducted as a double-blind, randomized, parallel-group, vehicle-controlled, multicenter trial.

[figure not shown]
Approximately [REDACTED] healthy males and females, 12 to 40 years of age, inclusive, who meet the inclusion/exclusion criteria, will be enrolled to obtain approximately [REDACTED] modified-Intent-To-Treat (mITT) and [REDACTED] per-protocol (PP) subjects. [REDACTED]

The actual number of subjects enrolled in the study will be based on blinded review of subject status (related to the per-protocol definition, [section 4](#)) to determine that the number of subjects expected to meet the PP criteria is sufficient [REDACTED]. If this number is expected to be met prior to enrolling [REDACTED] subjects, the enrollment will be closed.

Each subject will be randomly assigned to one of following treatment groups in a [REDACTED] ratio:

- (1) Test: Clindamycin Phosphate and Benzoyl Peroxide Topical Gel 1.2%/3.75%, [REDACTED]

(2) Reference: Onexton™ Topical Gel (Clindamycin Phosphate and Benzoyl Peroxide Gel 1.2%/3.75%), Valeant Pharmaceuticals North America, LLC
(3) Vehicle of test product Perrigo UK FINCO, [REDACTED]

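### The protocol prints one fixed block length of seven, so site staff can infer block membership; if each block holds a single vehicle, identifying that subject shows the other six are active

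*Protocol*

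**What the plan says.** Protocol 6.2.4 (Randomization) sets a block scheme "with each block of seven subjects assigned to Test: Reference: Vehicle"; the ratio that follows is blacked out. The SAP's Study Design section likewise says "Each subject will be randomly assigned to one of following treatment groups in a" and the figure is blacked out there too. No legible text varies the block length.

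Three other provisions bear on what a site can see:

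- Retention (Protocol 6.2.2): each dispensing site is "required to randomly select one block of study medication", and "The investigator will maintain one randomly selected block of study medication for each shipment of study medication received".
- Dispensing order (Protocol 6.2.1): "The individual boxes are numbered sequentially and should be dispensed in order".
- Numbering (Protocol 5.2): "The subject number will be taken from the study medication kit dispensed to the subject at each site".

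Protocol 6.2.5 allows a code break at the site in an emergency: "the specific subject treatment may be identified by removing the overlay of the blinded label for each subject at each investigator site".

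The safeguards are these. Protocol 6.2.1 states that "The investigator performing the clinical evaluations will not dispense or collect study medication". Section 5.2 calls for an independent third-party dispenser, but only where possible. Section 6.2.4 has an independent third party hold the code.

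**The concern.** Blocking balances the arms over time. If site staff know the block length and can see where blocks begin, learning one subject's treatment also tells them something about the other subjects in that block. Here the length is printed in the document that investigators work from. The retention procedure has sites pick out a block, and the kit numbers, which become the subject numbers, run in sequence.

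The lesion counts (Protocol 5.9) and the IGA (Protocol 5.8) are investigator judgements, made as far as possible by the same investigator at every visit. An evaluator who believes that the remaining subjects in a block are all active could score them more favourably. The superiority comparisons against vehicle (Protocol 8.1.4, SAP 5.5.1 and 5.5.2) are where such a shift would appear. An opened label leads to that subject's discontinuation (Protocol 6.2.5), but the protocol does not address what the opening reveals about the rest of the block.

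**Working it through.** **Inputs.** The block length is 7 (Protocol 6.2.4). The split within a block is not legible, so it is treated as an assumption and a range is shown. Neither document gives a figure for predictability, so there is nothing of the plan's own to reproduce.

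**Step 1: possible splits.** With all three arms present, 15 whole-number Test:Reference:Vehicle splits sum to 7, and 5 of them have exactly one vehicle. Three have equal active arms: 3:3:1, 2:2:3 and 1:1:5.

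**Step 2: one vehicle subject becomes known.** With v vehicles per block, each other subject's chance of vehicle goes from v/7 to (v − 1)/6.

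| Split | Vehicle, before | Vehicle, after | Active, before and after |
|---|---|---|---|
| 3:3:1 | 1/7 = 14% | 0/6 = 0% | 86% to 100% |
| 2:2:3 | 3/7 = 43% | 2/6 = 33% | 57% to 67% |
| 1:1:5 | 5/7 = 71% | 4/6 = 67% | 29% to 33% |

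Only the first row gives certainty. Under 3:3:1 the vehicle subject is equally likely to hold any of the seven places, so on average (6 + 5 + 4 + 3 + 2 + 1 + 0)/7 = 3.0 of the other six are enrolled after that subject.

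**Step 3: one active subject becomes known (3:3:1).** Each other subject's chance of vehicle goes from 1/7 = 14% to 1/6 = 17%. An opened label is vehicle one time in seven under this split, so this smaller shift is the usual result of a code break.

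**Step 4: Test against Reference.** When a vehicle subject is identified, the three Test and three Reference places under 3:3:1 are untouched, and an active subject is Test with probability 3/6 = 1/2, as before. The same 1/2 holds under 2:2:3 and 1:1:5. Opening a Test label under 3:3:1 leaves 2 Test, 3 Reference and 1 vehicle, so Test among the remaining actives falls from 1/2 to 2/5. That is a modest shift and identifies nobody.

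**Step 5: effect of a longer block.** In a block of 14 split 6:6:2, identifying one vehicle leaves 12 actives among 13, so the chance of active goes from 12/14 = 86% to 12/13 = 92% rather than 100%.

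**Step 6: can a site place subjects in blocks?** The length is printed, boxes are used in numerical order, and the subject number comes from the kit. A site that can tell where one block starts can count the others off in sevens. Selecting a block for retention implies that blocks are recognisable on site. This is an inference, since some packaging detail in Protocol 6.2.2 is blacked out.

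**The case against.** The strongest reply is that the route from block length to biased scores is long and partly guarded. The evaluating investigator neither dispenses nor collects medication. Emergency opening is confined to medical need, with prior authorization sought where possible and immediate notice to the sponsor. Retained kits are never dispensed, so retention can show block boundaries but no subject's treatment. All of this stands, and it lowers the risk. It does not remove it: third-party dispensing is qualified in Protocol 5.2, and the evaluator can still see subject numbers that come from the kits.

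The reply also disposes of some stronger readings that a reader might infer:

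- *Side effects give the vehicle subject away.* Protocol 4.4 mentions bleaching and local skin reactions, but these point to an active subject, which is the 14% to 17% case. Vehicle would have to be guessed from the absence of signs. Protocol section 7 puts contact dermatitis, application site burning, application site pruritus and rash at 0.4% each on the reference product, so the absence of a reaction says little.
- *Sites dispense whole blocks in sequence.* The text does not say this. Whole blocks are selected for retention; individual boxes are dispensed in order.
- *The seventh subject can be known to be vehicle.* Under 3:3:1 the chance would go from 14% to 100% only if all six others were correctly known to be active.

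A last objection is that deleting the number hides little while sites still handle recognisable seven-kit units. That is correct, and it limits what rewording alone can achieve.

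**Conclusion.** The point holds in conditional form. The fixed length, the retention procedure and the ordered dispensing together let site staff infer block membership. If the allocation places one vehicle in each block of seven, identifying that subject, for example by an emergency label opening, makes the other six known actives (86% to 100%).

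A reader might conclude that one identified vehicle always reveals the rest of the block. The documents do not support this, because the ratio cannot be read; under 2:2:3 or 1:1:5 each other subject would still be 33% or 67% likely to be vehicle. The blacking-out is not itself a fault in the plan. Nor do the documents support a claim that the equivalence comparison is compromised: with equal active arms, identifying a vehicle subject leaves Test and Reference indistinguishable.

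The exposure is therefore to the superiority comparisons. Its effect on the scores cannot be quantified from the documents, which give no frequency of unblinding. This is a cheap improvement to the protection of the blind. It is not an error or a contradiction in the plan.

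**What to change.** 1. In Protocol 6.2.4, keep the statement that randomization is blocked, remove the block length, and hold it in the third party's restricted randomization specification.
2. In Protocol 6.2.2, describe the retention sample as a randomly selected shipping unit, without identifying it as a randomization block.
3. If kits are not yet packed, also vary the block length, for example 7 and 14. Sites could then no longer count blocks off in sevens. Under a 3:3:1 ratio, identifying one vehicle in a 14-kit block would leave the others at 92% rather than 100% active.

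Items 1 and 2 are wording changes and give partial protection only. Item 3 needs a new kit list and a larger retention unit wherever a 14-kit block is drawn. If kits are already packed, items 1 and 2 are what remains practicable.

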6.2.5 Procedure for Breaking the Blind

The investigator, staff at the study site, study monitors, and data analysis/management personnel are blinded to the subject assignment. In the event of an emergency, the specific subject treatment may be identified by removing the overlay of the blinded label for each subject at each investigator site, which is attached to the study medication log; however, every effort should be made to maintain the blind. **The investigator must not scratch off the occluding layer of the label unless absolutely necessary to provide medical treatment to a subject in an emergency situation only and should seek prior authorization by Perrigo or designee when possible.** The reason for breaking the blind must be clearly documented in the source documentation and CRF and the subject must be discontinued from the study. Perrigo must be notified immediately upon all unblinding situations.

